6.5 Missing data

In the primary efficacy analysis (FDA Snapshot), participants with missing data at analysis time points will be considered as having lost undetectable plasma HIV-1 RNA levels. The analyses of overall patient disposition will show the number of patients who did not attend each protocol-defined visit.

For all continuous efficacy and safety variables, we will use, in the mITT population, the LOCF (last observation carried forward) approach to deal with missing data. We will also use mixed model as a sensitivity analysis.

For patients reported outcomes, we will use multiple imputation approach to fill in missing data.

6.6 Interim analysis

One administrative statistical interim analysis is planned on the primary efficacy endpoint to show whether the efficacy of the dual therapy with DTG and RPV is above 96% after week 24. This interim analysis is planned to take place when 120 participants (80 in the DTG/RPV arm and 40 in the control) have reached the 24-week visit. It will be done following week 24 with the mITT population. The 95% two-sided confidence interval of the percentage of patients in therapeutic success will be calculated and DTG/RPV will be considered as an acceptable strategy if the lower bound is greater than 87%. The strategy will be considered unacceptable if there are 18 therapeutic failures or more. With 18 failures among 80 subjects in the DTG/RPV arm, the observed proportion of success is 77.5% and the associated CI is 66.7% to 86.1%, so just excluding 87%. Additional issues could include treatment

emergent drug resistance, serious adverse events or high rates of discontinuation for adverse events. The interim analysis will also explore whether the lower limit of the 95% confidence interval of the difference in the percentage of participants with therapeutic success between the DTG/RPV arm and the control arm (DTG/RPV- control) remain in acceptable range (above -13%).

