6.20 End of trial

The end of the trial is defined as the date of the last visit (i.e. Follow-up visit) of the last subjects undergoing the trial.

CONFIDENTIAL

The sponsor must notify the Competent Authority and main REC of the end of a clinical trial within 90 days of its completion.

Note: The DSMB will elect stopping criteria as defined in the DSMB charter. If the study ends early by recommendation from the DSMB or for any other reason, the sponsor will notify the Competent Authorities and Ethics Committees of the reasons for the premature termination.

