9.5 Interim analysis

An interim analysis will be performed when 120 participants reach the week 24 visit (corresponding to 80

CONFIDENTIAL

participants in the DTG/RPV arm and 40 participants in the control arm). This will include a primary efficacy analysis for the Per Protocol population, excluding participants with serious protocol violations which could interfere with the reliability of the efficacy outcome. This analysis will be conducted to check the reliability of the results from the primary efficacy analysis and will also include the number of patients that discontinued the study due to adverse event or death, and discontinued the study for other reasons.

In the ANRS 163 ETRAL trial (Katlama et al., JAC 2019), in which 10% of participants harboured viruses with K103N mutation, the proportion of participants in success at week 24 with a dual therapy with etravirine and raltegravir was estimated at 96.4% (95%CI 92.3 to 98.7). Therefore, for this interim analysis at week 24: The expected level of efficacy is 96%, and the unacceptable level of efficacy (p_0) is 87%. With $\alpha = 5\%$ (unilateral) and 80% power, if we include 80 participants in the DTG/RPV arm, we will consider that the treatment is effective to be continued if there are no more than 4 failures. We test the null hypothesis $H_0: p \leq 87\%$ versus the alternative hypothesis $H_a: p \geq 96\%$, with an 80% chance that the lower bound of the 95% confidence interval would exclude 87% if the true success rate (p) is 96%. This gives a 5% chance of continuing if $p = p_0$ and an 80% chance of continuing if $p \geq 96\%$.

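### The week-24 interim rule gives no consequence for 5 to 17 failures among 80, yet the printed chances of continuing assume that 5 or more means not continuing

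*SAP*

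**What the plan says.** **Two-way rule.** Protocol 9.5 (Interim analysis), repeated in SAP 5 (Sample Size calculation), takes 87% as the unacceptable and 96% as the expected week-24 success rate. With 80 participants in the DTG/RPV arm, "we will consider that the treatment is effective to be continued if there are no more than 4 failures". Both sections then give the chance of continuing as 5% at 87% and 80% at 96% or above.

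**Two cuts.** SAP 6.6 (Interim analysis) uses the two-sided 95% confidence interval for the success percentage. At the upper end, "DTG/RPV will be considered as an acceptable strategy if the lower bound is greater than 87"%. At the lower end, "The strategy will be considered unacceptable if there are 18 therapeutic failures or more". The reason given for 18 is that "the observed proportion of success is 77.5% and the associated CI is 66.7% to 86.1%, so just excluding 87"%. SAP 6.6 also says the analysis will explore whether the lower 95% limit of the difference between arms stays above -13%. SAP 6.6 and 6.8 call the interim analysis administrative.

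**Population.** Protocol 9.5: "This will include a primary efficacy analysis for the Per Protocol population". SAP 6.6: "It will be done following week 24 with the mITT population".

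**Who decides.** Protocol 6.20 (End of trial): "The DSMB will elect stopping criteria as defined in the DSMB charter". Protocol 9.6 (DSMB) bases decisions on stopping on efficacy and safety results taken together.

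**The concern.** A chance of continuing describes a rule in which every count leads either to continuing or to not continuing. Protocol 9.5 and SAP 5 print such chances, so they imply that a fifth failure ends continuation. SAP 6.6 does not carry this through: it withholds the word unacceptable until the eighteenth failure and attaches no consequence to the 13 counts in between.

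This is the week-24 check on virological risk for a two-drug regimen containing an NNRTI, in people with an NNRTI mutation. The risk table in Protocol 1.1 lists virological failure and resistance as risks, and states that the combination has not been studied in patients with known or suspected NNRTI resistance. If the middle band is handled in any way other than not continuing, the printed 5% and 80% do not describe the trial being run. The sponsor, ethics committees and the DSMB could each read the same result differently.

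The difference in population adds to this. SAP 3.2.1 counts discontinuation as therapeutic failure. The Per Protocol definition (Protocol 9.7, SAP 6.3.2) excludes some early discontinuations. The same participants can therefore give two different failure counts to hold against either cut.

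**Working it through.** **Inputs.** n = 80 in the DTG/RPV arm (Protocol 9.5, SAP 5, SAP 6.6). Cuts: at most 4 failures (Protocol 9.5, SAP 5) and at least 18 (SAP 6.6). Reference rates 87% and 96% (Protocol 9.5, SAP 5). The other true rates below are assumptions, shown as a range.

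**Step 1: reproduce the plan's interval.** SAP 6.6 names no interval method. With 18 failures, success is 62/80 = 77.5%. The exact (Clopper-Pearson) 95% interval is 66.8% to 86.1%; the SAP prints 66.7% to 86.1%. The exact method is therefore used below.

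**Step 2: place both cuts on that interval.**

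| Failures of 80 | Success | Exact 95% CI | SAP 6.6 status |
|---|---|---|---|
| 4 | 95.0% | 87.7% to 98.6% | acceptable (lower limit above 87%) |
| 5 | 93.75% | 86.0% to 97.9% | neither |
| 10 | 87.5% | 78.2% to 93.8% | neither |
| 17 | 78.75% | 68.2% to 87.1% | neither |
| 18 | 77.5% | 66.8% to 86.1% | unacceptable |

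SAP 6.6's acceptable criterion is thus the 4-failure cut of Protocol 9.5 and SAP 5. Eighteen is the first count whose whole interval lies below 87%. Each cut is arithmetically right. What is missing is the decision between them.

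**Step 3: probability of each band.** X = number of failures, binomial with n = 80 and failure probability 1 - p, where p is the true success rate.

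| True success p | P(X ≤ 4) | P(5 ≤ X ≤ 17) | P(X ≥ 18) |
|---|---|---|---|
| 96% | 78.4% | 21.6% | 0.0% |
| 95% | 62.9% | 37.1% | 0.0% |
| 90% | 8.8% | 91.1% | 0.1% |
| 87% | 1.7% | 97.0% | 1.3% |
| 85% | 0.5% | 94.7% | 4.8% |
| 80% | 0.0% | 67.1% | 32.9% |
| 75% | 0.0% | 26.4% | 73.6% |

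**Step 4: compare with the printed chances of continuing.**

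- Two-way rule, continue at 4 or fewer: 1.7% at 87% (printed 5%) and 78.4% at 96% (printed 80%).
- Continue unless unacceptable, that is at 17 or fewer: 100% - 1.3% = 98.7% at 87%.

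The printed figures can belong only to the first reading. Even there the 5% is a ceiling that the rule does not reach: allowing 5 failures would give 4.3% at 87% and 89.9% at 96%.

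**The case against.** **The cuts do not contradict each other.** A reader might infer that SAP 6.6 replaces the 4-failure rule with an incompatible one. Step 2 shows otherwise. SAP 6.6 restates that cut and adds a futility-type boundary from the same interval, and at 10 failures it calls the strategy not acceptable as well as not unacceptable. This stands. The defect is an undefined middle band plus probabilities that presuppose there is none.

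**The 18-failure cut is not the only numerical check.** SAP 6.6 also has the -13% limit. By SAP formula (A), with 38 of 40 control successes and 8 failures in the DTG/RPV arm, the difference is 90% - 95% = -5.0%. The standard error is √(0.90×0.10/80 + 0.95×0.05/40) = 4.81%, so the lower limit is -5.0% - 1.96×4.81% = -14.4%. With 7 failures it is -12.9%. The limit is therefore breached from 8 failures; for control results from 36/40 to 40/40, from 10 down to 6. At 80% true success in the DTG/RPV arm, with assumed true control success of 90% to 100%, a breach has probability 94% to 99.9%. This stands as a fact about the plan, but the check is only to be explored and has no action attached, so it does not fill the gap.

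**The DSMB decides.** Protocol 9.6 gives stopping to a combined evaluation, and the charter may treat the middle band explicitly. That is possible and cannot be checked here. A charter would still leave Protocol 9.5, SAP 5 and SAP 6.6 saying different things, and the printed chances would still be wrong for any rule but the two-way one.

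**It is an administrative look in a pilot study.** Protocol 9.5 and SAP 5 nevertheless tie it to continuing, and Protocol 9.6 links DSMB review to decisions on stopping.

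**Population.** Protocol 9.5 says the interim will include a Per Protocol analysis, and the 4-failure sentence names no population. This is ambiguity rather than flat contradiction, but the set in which failures are counted is still not fixed.

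**Conclusion.** The inconsistency is real. Counts of 5 to 17 have no stated consequence beyond general DSMB judgement, while the printed 5% and 80% require that they mean not continuing. The band is not marginal: it takes 97.0% of outcomes at the rate the plan calls unacceptable and 21.6% at the rate it expects.

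A reader might go further and infer that a poor arm would usually not be stopped. The documents do not support that. SAP 6.6 says unacceptable and never says stop, other criteria feed the decision, and the 18-failure cut taken alone is reached in 32.9% of trials at 80% true success and 73.6% at 75%.

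The conclusion assumes 80 evaluable participants in the DTG/RPV arm, independent outcomes, and the exact interval that reproduces the SAP's figure. A Wilson interval gives the same upper cut; a simple Wald interval would move it to 5 failures (lower limit 88.45%). Neither choice closes the gap. The contents of the DSMB charter are unknown.

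**What to change.** Reconcile Protocol 9.5, SAP 5, SAP 6.6 and the DSMB charter before interim data are reviewed:

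1. State one rule in one form, naming the interval method if the rule is written through an interval.
2. Name one population for the failure count.
3. Give the consequence of every count from 0 to 80, including who decides at 5 to 17 and on what basis, and say how the -13% check enters the decision.
4. Make the probabilities match. If the two-way rule at 4 failures is kept, print its exact chances of continuing (1.7% at 87%, 78.4% at 96%). If three zones are kept, replace that sentence with the probability of each zone over a range of true rates, as in Step 3.

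Which rule to adopt is for the sponsor and the DSMB. The cost is wording in the protocol, SAP and charter, with no extra participants or data. With three zones, the stated operating characteristics will look less favourable than the ones now printed.

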6.7 Multi-centre Studies

Potential centre effects will not be taken into account in the analyses, as randomisation should make the two populations similar in all respects.

6.8 Multiple testing

As only an administrative interim analysis will be conducted, no multiplicity adjustment is required.

[figure not shown]
7. Summary of Study Data

All continuous variables will be summarized using the following descriptive statistics: n (non-missing sample size), mean, standard deviation, 1st quartile, median, 3rd quartile, maximum and minimum. The frequency and percentages (based on the non-missing sample size) of observed levels will be reported for all categorical variables.

7.1 Subject Disposition

The number of patients and the flowchart of the study will be presented. The period of enrolment and the total number of patients screened to be included in the study will be presented. The number of ineligible patients and the total number of randomised patients will be presented. The number of patients who never take the study treatment will also be presented by group and the reasons will be given and those who remained on the study treatment up to week 48 and 96 will be presented. The number of patients who discontinued the study will be presented and the reasons of discontinuation as well as the time from randomisation to discontinuation will be given. All these information will be shown in the study Flowchart as below (Figure 1).

Figure 1: Study Flowchart

7.2 Protocol Deviations

The following violations are defined as protocol deviations for the purpose of analysis: The deviation might be related to:

- (a) Eligibility;
- (b) Study related assessments;
- (c) Social history;
- (d) PK sampling;
- (e) Drug dispensing;
- (f) Adherence;
- (g) Follow up (lost to follow-up,);
- (h) Other (consent withdrawal, giving up, ...)

The following violations will be considered as a serious deviation for the purpose of analysis: Patients who will not take study treatment; Interruptions of study drug for >10% of total time on treatment; Patient who will not fulfil the eligibility criteria; Patients who will withdraw the consent; Patients who will not comply with their randomization arm; Patients with missing value at the primary endpoint evaluation: Patient who will be lost to follow-up.

A patient will be considered lost to follow-up when he/she will not come to more than 2 visits of the

protocol. Patients who cannot be contacted on or before the last scheduled visit prior to the week 96 and who will not have a known reason for discontinuation (eg, withdrew consent, giving up, etc.) will be classified as “lost to follow-up”.

Patients will be considered in discontinuation of the study when they will refuse to continue the follow-up of the study.

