6.19 Virological failure

Virological failure is defined as two consecutive measurements of plasma viral load above 50 copies/ml separated by at least 14 days during the assigned treatment. Note: If the initial sample analysis returns result of >50c/mL, the remainder of the sample should be re-analysed, if possible. Only if the repeat analysis produces a second result of >50c/mL, or if re-analysis is not possible, the patients should be recalled for retesting. The remainder of the retesting sample should be analysed if the retesting analysis produces a result of >50c/mL. In case of virological failure a resistance study will be conducted in the local lab of each centre. Note: resistance test should be performed from the suspect virological failure visit sample and from the confirmatory visit when available.

Pharmacokinetic testing should also be carried out in the event of viral failure.

Patients should discontinue study medication and receive rescue medication at investigators discretion.

Therapeutic failure includes virological failure, change in treatment for any reason, consent withdrawal, loss to follow-up or death.

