9.2.3 Secondary outcome analysis

Primary efficacy analysis repeated with (<200 copies/ml HIV RNA) at 24, 48, 96.

The primary efficacy analysis will be repeated for the Per Protocol population, excluding participants with serious protocol violations which could interfere with the reliability of the efficacy outcome. Examples would include taking other antiretroviral treatment within the first 48 weeks of treatment, incorrect randomisation or early discontinuation from the study for reasons unconnected to efficacy or safety. This analysis will be conducted to check the reliability of the results from the primary efficacy analysis.

In addition, a “Switch Included” analysis will be conducted, to check the outcomes of participants who discontinued randomised treatment for any reason. This analysis will follow the same methods as FDA Snapshot, but will include HIV RNA data from all participants with results available at Week 48, whether they are on or off randomised treatment. There will be no formal non inferiority outcome analysis as this is a pilot study.

All analysis details will be included in Statistical Analysis Plan.

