3.2 Study endpoints

3.2.1 Primary endpoint/outcome

The primary endpoint is the proportion of participants free of therapeutic failure at week 48 (HIV RNA <50 copies/mL and no discontinuation). Therapeutic failure is defined as virologic failure or discontinuation with HIV RNA <50 copies/mL. Discontinuation is defined by the study follow-up stop or any change or modification in the study treatment regimen.

The following procedure will be used to classify the participants.

1. Virological failure:

- (a) Any patient with HIV RNA levels ≥ 50 copies/mL at any time points will have a repeat test on a second measurement within 2 weeks apart. If the result from the second measurement is <50 copies/mL, the patient will be categorized as HIV-RNA <50 copies/mL. If the result from the second measurement is ≥ 50 copies/mL, the patient will be categorized as virological failure.
- (b) If a patient has HIV-RNA ≥ 50 copies/mL at a given time point and stops the study or at least one drug from the study treatment combination for any reason, he or she will be categorized as virological failure.
- (c) If a patient discontinues the study or at least one drug from the study treatment combination at a given time point because of lack of efficacy then the patient will be categorized as virological failure.

2. Discontinuation (no virological data)

All discontinuations with HIV RNA <50 copies/mL will be considered as no virological data. There are three main reasons for no data at analysis time point:

- (a) Discontinuation due to Adverse Event (AE) or Death.

Any patient who discontinues the study or the study treatment with HIV-RNA is < 50 copies/mL because of AE or death will be classified as discontinuation due to AE or death at from the date of discontinuation.

(b) Discontinuation for Other Reasons.

If a patient discontinues the study follow-up or changes or modifies any drug in the study treatment when his or her HIV-1-RNA is < 50 copies/mL, he or she will be categorized as discontinued for other reasons at from the date of discontinuation.

(c) On study but missing data at analysis time point.

For example, if a participant has no data at analysis time point, but there is an HIV-RNA measurement after the analysis time point, this patient will be considered On Study but with Missing Data at analysis time point.

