6.3.2 Per-Protocol Population

The per-protocol population will include all patients from the mITT population, excluding participants with serious protocol violations which could interfere with the reliability of the efficacy outcome. Examples would include taking other antiretroviral treatment during the course of the study, incorrect randomisation or early discontinuation from the study for reasons unconnected to efficacy or safety. This analysis will be conducted to check the reliability of the results from the primary efficacy analysis.

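### The per-protocol exclusions overlap with the definition of failure and conflict with each other, so the per-protocol analysis cannot check the discontinuation and missing-data part of the primary result

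*SAP*

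**What the plan says.** **What counts as failure.** SAP 3.2.1: "Therapeutic failure is defined as virologic failure or discontinuation with HIV RNA <50 copies/mL". Discontinuation there includes any change to the study regimen. SAP 6.5 adds, for the primary analysis, that "participants with missing data at analysis time points will be considered as having lost undetectable plasma HIV-1 RNA levels". SAP 8.1 uses only values taken on treatment and on trial.

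**Who leaves the per-protocol set.** SAP 6.3.2 starts from the mITT population, "excluding participants with serious protocol violations which could interfere with the reliability of the efficacy outcome". Its examples are "taking other antiretroviral treatment during the course of the study, incorrect randomisation or early discontinuation from the study for reasons unconnected to efficacy or safety". Protocol 9.2.3 and 9.7 give the same examples, except that the antiretroviral item reads "taking other antiretroviral treatment within the first 48 weeks of treatment".

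**What counts as a serious deviation.** SAP 7.2 lists never taking study treatment, interruption for more than 10% of treatment time, ineligibility, consent withdrawal and non-compliance with the randomised arm. The list ends with "Patients with missing value at the primary endpoint evaluation: Patient who will be lost to follow-up". None of these items is limited by reason.

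**After virological failure.** Protocol 6.19: "Patients should discontinue study medication and receive rescue medication at investigators discretion".

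**Purpose and interim use.** SAP 6.3.2 gives the analysis the task of checking the reliability of the primary result. SAP 6.4.1 and Protocol 9.3 assign that task to it together with the Switch Included analysis. On the interim, Protocol 9.5 states: "This will include a primary efficacy analysis for the Per Protocol population". SAP 6.6 runs the interim on mITT.

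**The concern.** Several events that make a participant a failure in mITT also remove that participant from the per-protocol set. Membership then depends partly on the outcome, and per-protocol success moves upward in both arms. If one arm has more AE stops or more missing values, the difference between arms shrinks as well. A per-protocol result close to zero could then be read as support for the primary result when it reflects only who was removed.

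The rules also conflict. The discontinuation wording in SAP 6.3.2 implies that efficacy and safety failures stay in. The unqualified missing-value item in 7.2 and the unqualified antiretroviral item in 6.3.2 can take them out. No text says which prevails, so in an open-label trial membership could be settled after outcomes are known.

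The SAP's wider time window adds a second problem. A week-48 success who changes antiretrovirals at, say, week 70 can be removed by an event after the endpoint. SAP 6.1 places the primary analysis before the week-96 analysis, so the week-48 per-protocol set could differ between the two reports.

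**Working it through.** **Step 1. The plan's own figure.** The documents give no per-protocol figure. The nearest is the planning table in Protocol 9.1 and SAP 5: lower 95% bounds from −7.4% to −9.3% for 95% success on DTG/RPV (n=100) against 95% to 100% on control (n=50). Formula (A) in SAP 8.1 is (p1 − p2) ± 1.96 × √(p1q1/n1 + p2q2/n2).
- 95% vs 95%: 0 − 1.96 × √(0.95×0.05/100 + 0.95×0.05/50) = −7.4%.
- 95% vs 100%: −5.0% − 1.96 × √(0.95×0.05/100) = −9.3%.

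Both lower bounds reproduce, so formula (A) is used below.

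**Step 2. The rules side by side.**

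| Event before week 48 | mITT | SAP 6.3.2 discontinuation wording | SAP 7.2 list and 6.3.2 antiretroviral item |
|---|---|---|---|
| Death, or AE stop with no week-48 value | failure | stays, as failure | leaves (missing value) |
| AE stop with switch to other antiretrovirals | failure | stays, as failure | leaves (other antiretroviral) |
| Missing or lost, unconnected to efficacy or safety | failure | leaves | leaves |
| Virological failure, then rescue | failure | stays, as failure | leaves only on the most literal reading |

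**Step 3. Illustration with an assumed failure mix.** The documents give no mix. Assume:
- DTG/RPV, of 100: 2 virological failures, 8 AE switches, 5 missing for unconnected reasons, hence 85 successes.
- Control, of 50: 1 virological failure, 1 missing, hence 48 successes.

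| Set | DTG/RPV | Control | Difference (95% CI), points |
|---|---|---|---|
| mITT | 85/100 = 85.0% | 48/50 = 96.0% | −11.0 (−19.9 to −2.1) |
| Per-protocol, efficacy and AE failures kept | 85/95 = 89.5% | 48/49 = 98.0% | −8.5 (−15.8 to −1.2) |
| Per-protocol, missing and AE switches dropped, virological failures kept | 85/87 = 97.7% | 48/49 = 98.0% | −0.3 (−5.3 to 4.8) |

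The move from the first row to the second is what any set that drops unconnected losses would show. The move from the second to the third comes from the unqualified rules.

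**Step 4. How far the mix matters.**
- *Heavier loss.* Protocol 6.12 expects 15% loss to follow-up, without naming a week. Assume DTG/RPV has 2 virological failures, 3 AE switches and 15 missing of 100, and control has 1 virological failure and 8 missing of 50. mITT is 80.0% vs 82.0%, −2.0 (−15.2 to 11.2). With efficacy and AE failures kept, per-protocol is 80/85 = 94.1% vs 41/42 = 97.6%, −3.5 (−10.3 to 3.3). With AE switches also dropped it is 80/82 = 97.6% vs 97.6%, −0.1 (−5.8 to 5.6).
- *All failures virological.* With 5 of 100 and 1 of 50, mITT is 95.0% vs 98.0%, −3.0 (−8.8 to 2.8). Per-protocol with virological failures kept is identical.

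**Step 5. The interim.** Protocol 9.5 and SAP 5 continue if there are no more than 4 failures among 80 on DTG/RPV. Assume 3% virological and 10% non-virological failure, so that true success is 87%, the level that the documents call unacceptable. Apply the exclusions at week 24.
- All failures counted: P(X ≤ 4), X ~ Bin(80, 0.13) = 1.7%.
- Only virological failures counted, limit still 4: P(X ≤ 4), X ~ Bin(80, 0.03) = 90.7%.
- With a 5%/8% split the second figure is 62.9%. With 2%/15% (true success 83%) the two figures are 0.1% and 97.8%.

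**The case against.** The strongest case on the other side has five parts.

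1. *Virological failures stay in.* Confirmed HIV RNA at or above 50 copies/mL is on neither exclusion list. SAP 6.3.2 removes protocol violations, and rescue after virological failure is what Protocol 6.19 directs, so it is arguably not a violation. This stands. A reader might infer from the antiretroviral item that every failure is removed and that both arms go to 100%. That needs the most literal reading, and the discontinuation wording in the same sentence of 6.3.2 points against it. The 7.2 list alone does not produce 100% either, since a virological failure with a measured value is not missing.

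2. *The colon in SAP 7.2.* The other items are separated by semicolons. The colon may define a missing value as loss to follow-up, which 7.2 describes for uncontactable patients as having no known reason for discontinuation. Deaths and AE stops with a known reason would then stay in. This reading is possible. The text does not settle it, and it leaves the antiretroviral item untouched.

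3. *No cross-reference.* Nothing formally ties the serious deviations of 7.2 to the serious violations of 6.3.2. True, but 7.2 defines them for the purpose of analysis, and the per-protocol set is the population defined by excluding serious violations. The link is a strong inference.

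4. *Other analyses limit the damage.* The primary analysis is mITT with missing counted as failure, SAP 8.2.1 analyses virological failure over 96 weeks in mITT, Switch Included uses week-48 results on or off treatment, and no formal non-inferiority conclusion is drawn. All true. This limits the consequence but does not give the per-protocol analysis the function that 6.3.2 assigns to it.

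5. *AE stoppers and other antiretrovirals.* The documents do not say that every AE stopper starts another regimen. Hence the AE switches above are an assumption.

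**Conclusion.** The concern holds in a limited form. Events that are failures in mITT can become per-protocol exclusions, against the SAP's own limit to reasons unconnected to efficacy or safety. The SAP also extends the antiretroviral exclusion past the protocol's 48 weeks. Per-protocol success is biased upward, and the analysis cannot check the discontinuation and missing-data part of the primary result.

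A reader might go further and infer that the analysis checks nothing, or would confirm similarity whatever the data show. The documents do not support that: if virological failures are kept, the virological part is still checked, and when all failures are virological the per-protocol and mITT results coincide.

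The size depends on the failure mix. In the main illustration the unqualified rules move the difference from −8.5 to −0.3 points, and an interval that excluded zero no longer does. With no AE or missing-data failures there is no shift. The conclusion assumes that the 7.2 list feeds the 6.3.2 exclusions and that the missing-value item stands on its own. The interim figures apply only if the interim is run on the per-protocol set, as Protocol 9.5 says and SAP 6.6 does not.

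**What to change.** In SAP 6.3.2 and 7.2:

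1. Keep virological failure and discontinuation for AE, death or lack of efficacy in the per-protocol set as failures, with or without a week-48 value.
2. Do not count as violations any antiretroviral changes or interruptions that result from a failure or an AE.
3. For the week-48 analysis, use only deviations up to week 48, in line with Protocol 9.2.3 and 9.7.
4. Exclude a missing week-48 value or loss to follow-up only when the reason is unconnected to efficacy or safety. Separate the two items in 7.2 and cross-refer 7.2 to 6.3.2.
5. Reconcile the interim population between Protocol 9.5 (per-protocol) and SAP 6.6 (mITT).

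Items 1 to 4 need SAP wording only; item 5 needs the two documents brought into line. Per-protocol success will look slightly less favourable, and the reasons for missing values must be reviewed and classified before database lock.
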